### **Reporting in eCRF**

At each visit, the site staff will record the following in the eCRF: Date and time of blood sample (or that a blood sample was not taken) and the investigator's assessment of the results ('normal', 'abnormal, not clinically significant', 'abnormal, clinically significant'). In addition, the site staff will record in the eCRF if a urine sample was taken and the investigator's assessment of the result ('normal', 'abnormal').

Clinically significant abnormal laboratory findings at the (first) screening visit will be documented as medical history in the eCRF. If an abnormal laboratory finding at any other visit than the first screening visit is considered by the investigator to be clinically significant, it will be reported as an AE in accordance with Section [13.3](#). Further, any clinically significant deterioration of a pre-existing condition as well as any new clinically significant sign, symptom or illness observed after screening will be reported as an AE in accordance with Section [13.3](#).

### **11.4.6 Anti-drug antibodies measurements**

Blood samples will be collected for determination of anti-tralokinumab antibody levels at pre-determined time points according to the schedule of trial procedures (Section [4](#)).

It will be recorded in the eCRF if the ADA sample was taken; if not, a reason will be provided.

Collection, handling and shipment instructions for ADA blood samples are provided in a separate laboratory manual.

Serum samples for determination of presence or absence of ADA will be analysed by a laboratory using a validated bioanalytical method. A tiered testing scheme will be employed, with the first step being screening. Samples found positive in the screening step will be tested in the confirmatory step. Samples confirmed positive for ADA in the confirmatory step will undergo endpoint titre determination and will be analysed for the presence of neutralising

antibodies (nAB). Details of the analytical method used will be described in the ADA bioanalytical report.

### **11.5 Assessment of vaccine responses**

Blood samples for assessment of vaccine-specific serum antibody responses will be collected at the time points specified in the schedule of trial procedures (Section 4).

Collection, handling and shipment instructions for these blood samples are provided in a laboratory manual.

The antibody response to Tdap vaccine will be assessed by measuring serum anti-tetanus IgG by an immunoassay. The antibody response to meningococcal vaccine will be assessed by measuring serum anti-meningococcal IgG by an immunoassay.

Reports of serum antibody responses will be provided by the laboratory to the trial sites at the end of the trial. The investigator must sign and date these reports.

#### **Reporting in eCRF**

It will be recorded in the eCRF if the blood samples to assess vaccine response were taken; if not, a reason will be provided.

### **11.6 Pharmacokinetic assessments**

Blood samples for PK assessments must be collected at the time points specified in the schedule of trial procedures (Section 4).

It will be recorded in the eCRF if the PK sample was taken; if not, a reason will be provided.

Collection, handling and shipment instructions for PK blood samples are provided in a laboratory manual.

Serum samples for determination of tralokinumab concentrations will be analysed by a laboratory using a validated bioanalytical method. Details of the analytical method used will be described in the bioanalytical report.

### **11.7 Pharmacodynamics and pharmacogenomics**

Not applicable.

## 11.8 Other assessments

Not applicable.

## 11.9 Estimate of total blood volume collected

Blood samples will be drawn for chemistry, haematology, serology, PK, ADA, and vaccine-specific serum antibody responses. The total volume of blood to be drawn is approximately 150 mL which is less than the volume of blood drawn during a blood donation (approximately 500 mL).

## 11.10 End of trial

An end-of-treatment form and an end-of-trial form will be completed in the eCRF for all randomised subjects, including subjects who permanently discontinue IMP and subjects who withdraw from trial (see Section 10.3 for early termination assessments).

### End-of-treatment form

An end-of-treatment form will be completed when the subject has had their last administration of IMP. The following data will be recorded on this form:

- Date of last administration of IMP (tralokinumab/placebo).
- Has the subject completed the treatment period (yes/no). If no, the primary reason for permanent discontinuation of IMP must be recorded (lack of efficacy, AE, withdrawal by subject, lost to follow-up, death, other).

The primary reason for permanent discontinuation of IMP must also be recorded in the medical records.

### End-of-trial form

An end-of-trial form will be completed when the subject has had their last visit. The following data will be collected:

- Did the subject complete the trial (yes/no).
- Has the subject been transferred to LP0162-1337 (yes/no). If yes, the site will record the last visit the subject attended, including phone calls (Week 16, Week 20, Week 24, Week 30, unscheduled visit).
- Did the subject attend the nominal Week 16 visit (yes/no). If no, the primary reason for not attending the visit must be recorded (lack of efficacy, AE, withdrawal by subject, lost to follow-up, death, other).

- Did the subject attend the safety follow-up visit (yes/no). If no, the primary reason for not attending the visit must be recorded (lack of efficacy, AE, withdrawal by subject, lost to follow-up, death, transferred to LP0162-1337, other).
- Date of last contact.
- Primary reason for withdrawal from trial (lack of efficacy, adverse event, withdrawal by subject, lost to follow-up, death, other).

### **11.11 Storage of biological samples**

The samples analysed by the central laboratory ([Panel 11](#)) will be destroyed after analysis.

PK samples will be retained for as long as the quality of the material permits evaluation but for no longer than 12 months after completion of the CTR.

Samples for ADA evaluation will be retained for as long as the quality of the material permits evaluation but for no longer than 15 years after marketing authorisation.

Samples collected to assess the vaccine-specific antibody response will be retained for as long as the quality of the material permits evaluation but for no longer than 12 months after completion of the CTR.

## 12 Scientific rationale for trial design and appropriateness of assessments

This trial will assess immunisation responses against 2 different vaccines (a combined diphtheria, tetanus, and acellular pertussis vaccine and a meningococcal vaccine) in adults with moderate-to-severe AD who are treated with tralokinumab, to ensure a broad assessment of immune competence in subjects treated with tralokinumab.

Since concomitant administration of vaccines may affect the efficacy of tralokinumab in patients with AD, a placebo-controlled parallel group design has been chosen to evaluate the efficacy and safety of Q2W tralokinumab concomitantly administered with vaccines in the target patient population.

The vaccines will be given after 12 weeks of tralokinumab/placebo treatment to ensure that the trial drug effect has reached near-steady state levels when the vaccines are administered.

The vaccine responses will be analysed at Week 16 when the tralokinumab/placebo treatment schedule is complete. This allows an evaluation of the vaccine responses 4 weeks after vaccination which is the time span used to evaluate efficacy of these vaccine products (33, 34).

The trial will evaluate the percentage of subjects achieving a positive anti-tetanus response at Week 16 (defined as a 3-fold IgG increase compared to Week 12 if  $\text{IgG} \leq 1.0 \text{ IU/mL}$  at Week 12; or  $\text{IgG} \geq 2.5 \text{ IU/mL}$  if  $\text{IgG} > 1.0 \text{ IU/mL}$  at Week 12) and a positive anti-meningococcal response at Week 16 (defined as  $\text{IgG} \geq 3.0 \text{ mcg/mL}$  with at least a 3-fold increase compared to Week 12). These response criteria were developed based on the criteria for positive vaccine response in the assays used for determining anti-tetanus and anti-meningococcal IgG concentrations. The anti-tetanus response definition takes into account that some subjects may have high pre-vaccination anti-tetanus IgG levels and may therefore not be able to elicit the same increase in anti-tetanus IgG levels as those with low pre-vaccination levels.

The results should be generalisable to an adult population with AD. The age limit of 54 years is chosen to ensure that no subjects older than the meningococcal vaccine age limit of 55 years are included.

Subjects who do not achieve or lose clinical response will not be excluded from further participation in the trial. This approach has been chosen to increase the likelihood that subjects from the placebo arm will stay in the trial until administration of the vaccines (Week 12) and evaluation of the vaccine responses (Week 16). Subjects who complete the

Week 16 visit may be invited for the open-label, long-term extension trial conducted under a separate clinical trial protocol (ECZTEND).

The clinical efficacy of tralokinumab treatment will be assessed by IGA, EASI, and SCORAD. IGA is a key instrument used in clinical trials to rate the severity of the subject's global AD. EASI is a validated measure used in clinical practice and clinical trials to assess the severity and extent of AD (26). SCORAD is a validated tool to assess the extent and severity of AD lesions and subjective symptoms (28).

The efficacy endpoints IGA score of 0 or 1 and EASI75 are recognised as important endpoints in clinical trials in AD by regulators in the US and EU, respectively.

Data on antibodies against tralokinumab (ADAs) will be collected and the potential for immunogenicity will be evaluated until 16 weeks after the last dose of tralokinumab, to ensure adequate washout (approximately 5 times the half-life). The serum samples for determination of presence or absence ADA will be analysed using a validated bioanalytical method.

Safety will be assessed using standard clinical methods of subject evaluations, such as AE monitoring, ECG, vital sign and clinical laboratory measurements.

## 13 Adverse events

### 13.1 Definition and classification of adverse events

Adverse events (AEs) and serious adverse events (SAEs) are defined in [Appendix 1](#).

Classification of AEs in terms of severity, causality and outcome is defined in [Appendix 2](#). A causality assessment will be made for both tralokinumab/placebo and each of the vaccines.

### 13.2 Collection of adverse event reports

AEs must be collected from time of first trial-related activity after the subject has signed the informed consent form (ICF) until completion of the clinical trial (defined as per [Section 7.3](#)).

AEs must be assessed by medically qualified personnel.

At all visits, the subject will be asked a non-leading question by the investigator about AEs, for example: “How have you felt since I saw you last?” No specific symptoms should be asked for. It is important that the investigator also observes the subject for any changes not reported by the subject and records these changes.

Refer to [Sections 11.4.1](#) to [11.4.5](#) for principles for data entry in the eCRF.

### 13.3 Reporting of adverse events

AEs reported by the subject or observed by the investigator must be recorded on the AE form of the eCRF and should be described in the following manner:

The *AE term* must be in precise English medical terminology (that is, not necessarily the exact words used by the subject). Whenever possible, a specific diagnosis should be stated (for example ‘allergic contact dermatitis’).

The *duration* of the AE must be reported by the start date and stop date of the event (it will also be recorded if the event is ongoing). In addition, it will be recorded if the AE started prior to first dose of IMP (tralokinumab/placebo); it will also be recorded if the AE started prior to administration of the vaccines.

AEs must be classified in terms of severity, causality and outcome according to the definitions in [Appendix 2](#).

*Action taken with IMP:* any action taken with IMP as a consequence of the AE must be recorded (dose not changed, dose reduced, dose increased, drug interrupted, drug withdrawn, not applicable, unknown).

*Other action taken:* any other action taken as a result of the AE must be recorded (none, concomitant medication, concurrent procedure).

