#### Screening period (Week -6 to Week 0)

The screening period has a minimum duration of 2 weeks and a maximum duration of 6 weeks and includes 1 or 2 screening visits. The exact duration of the screening period depends on the washout period defined by the exclusion criteria (Section 8.3). If a washout is not required, screening will be reduced to 2 weeks and only requires 1 visit (Week -2; visit 2), i.e., the 2 screening visits will be merged. Similarly, if only a 2-week wash-out is required, screening visits 1 and 2 will be combined (Week -2; visit 2). All subjects will attend a screening visit 14 days before baseline (Week -2; visit 2). Eligibility will be assessed at the (first) screening visit and on Day 0 prior to randomisation.

All subjects will use an emollient twice daily (or more, as needed) for at least 14 days before randomisation and will continue this treatment throughout the trial (including safety follow-up). Subjects will initiate emollient treatment no later than the Week -2 visit.

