#### **14.3.8.1 Adverse events**

AEs will be coded during the course of the trial according to Medical Dictionary for Regulatory Activities (MedDRA). AEs will be presented by preferred terms and primary system organ class (SOC).

Treatment-emergent AEs will be summarised, however, all AEs recorded during the course of the trial will be included in the subject data listings. An event will be considered treatment-emergent if started after the first use of IMP or if started before the first use of IMP (applicable if subject had a wash-out) and worsened in severity thereafter. The tabulations described in the following will only include the treatment-emergent events. In each of the tabulations, AEs will be defined by MedDRA preferred terms within primary SOC.

An overall summary of the number of treatment-emergent AEs, number (percentage) of subjects with any treatment-emergent AEs, SAEs, deaths, premature discontinuations from the trial due to AEs, treatment-related AEs and severe AEs will be presented.

The number of AEs and the number of subjects experiencing each type of AE will be tabulated by treatment group. The percentage of subjects with AEs will be compared between treatment groups by a chi-square test or Fisher's exact test (if expected cell count < 5).

The severity for each type of AE will be tabulated by treatment group.

The causal relationship to IMP (tralokinumab/placebo) for each type of AE will be tabulated by treatment group. Related AEs are defined as AEs for which the investigator has not described the causal relationship to IMP as 'not related'. The number of related AEs and the number of subjects experiencing each type of related AE will be tabulated. The percentage of subjects with related AEs will be compared between treatment groups by a chi-square test or Fisher's exact test (if expected cell count <5).

The causal relationship to IMP (each vaccine) for each type of AE will be tabulated by treatment group. Related AEs are defined as AEs for which the investigator has not described the causal relationship to IMP as 'not related'. The number of related AEs and the number of subjects experiencing each type of related AE will be tabulated. The percentage of subjects with related AEs will be compared between treatment groups by a chi-square test or Fisher's exact test (if expected cell count <5).

SAEs and AESIs will be evaluated separately and a narrative for each will be given. AEs leading to withdrawal from trial will be listed.

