6.8 Analysis of safety

6.8.1 Adverse events

AEs will be summarised and listed.

Assignment of AEs to periods

An AE will be assigned to a given period (treatment period or safety follow-up) if the start date is after the start date and before the end date of that period (see Section 6.9.2, Table 6).

For AEs with start day on the same day as the first dose was given, only AEs starting after the first dose was given will be considered treatment-emergent and assigned to the treatment period.

AEs starting on the day of exposure end (as defined in Section 6.9.2) will be assigned to the safety follow-up treatment period.

For handling of incomplete start dates of AEs, see Section 6.9.3.

Sort order of AE tables

Generally, AE tables by system organ class and/or preferred term will be sorted by decreasing number of affected subjects in the Tralokinumab group.

Other adverse events

A MedDRA search on all reported AEs was specified to capture AEs belonging to injection site reactions. The MedDRA search to capture this safety area of interest was performed using the following HLT levels (based on primary and secondary terms): ‘administration site reactions NEC’, ‘application and instillation site reactions’, and ‘injection site reactions.

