6.9.3 Incomplete recordings

Adverse events

If the AE start day is missing, but AE start month and year are not missing, the following rules apply:

- If the year and month of the AE start is before the year and month of the exposure start, or if the AE end date is complete and before the exposure start, the AE will not be considered treatment-emergent.
- If the year and month of the AE start is the same as the year and month of the exposure start, the AE will be considered treatment-emergent and assigned to the treatment period, unless the AE has a complete end date which is before exposure start.
- If the year and month of the AE start is after the year and month of exposure start, it will be assumed that the AE started on the first day of the month and the AE will be assigned to the treatment or safety follow-up period accordingly.

If the AE start month is missing, but AE start year is not missing, the following rules apply:

- If the year of the AE start is before the year of the exposure start, or if the AE end month is not missing and before the month of the exposure start, or if the AE has a complete end date which is before the exposure start date, the AE will not be considered treatment-emergent.
- If the year of the AE start is the same as the year of the exposure start, the AE will be considered treatment-emergent and assigned to the treatment period, unless the AE end month is not missing and before the month of the exposure start or the AE has a complete end date which is before the exposure start date.
- If the year of the AE start is after the year of exposure start, it will be assumed that the AE started on the 01 January and the AE will be assigned to the treatment or safety follow-up period accordingly.

Concomitant medication

For incomplete start dates of concomitant medication, the following rules apply:

- If a medication start day is missing, but start month and year are not missing, it will be assumed that the start day is the first day of the month. If the medication start day and

month are missing, but start year is not missing, it will be assumed that the start day is 01 January. If the medication start day, month, and year are missing, it will be assumed that the medication was started before trial start, and the date will appear as missing in the data.

For incomplete end dates of concomitant medication, the following rules apply:

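### SAP 6.9.3 classes some partially dated AEs as treatment-emergent even when the site has recorded that they began before the first dose

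*Protocol*

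**What the plan says.** Protocol 13.2 starts AE collection at consent: "AEs must be collected from time of first trial-related activity after the subject has signed the informed consent form (ICF"). Protocol 7.1 gives the interval before dosing: "The screening period has a minimum duration of 2 weeks and a maximum duration of 6 weeks". Pre-dose AEs will therefore be in the database.

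For timing, protocol 13.3 states that the duration "of the AE must be reported by the start date and stop date of the event". It then adds a separate item: "In addition, it will be recorded if the AE started prior to first dose of IMP (tralokinumab/placebo"). No AE start time is listed there.

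Protocol 14.3.8.1 defines the events to be tabulated: "An event will be considered treatment-emergent if started after the first use of IMP or if started before the first use of IMP" and worsened in severity afterwards. Appendix 2 (Severity) requires a worsened AE to be entered as a new AE.

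SAP 6.8.1 deals with onset on the day of first dose: "only AEs starting after the first dose was given will be considered treatment-emergent and assigned to the treatment period". It refers incomplete start dates to SAP 6.9.3. There, when the day is missing and the start month is that of first dose, "the AE will be considered treatment-emergent and assigned to the treatment period, unless the AE has a complete end date which is before exposure start". A parallel rule covers a missing month in the same year; its exceptions rest only on the end month or end date. Neither section mentions the pre-dose item.

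**The concern.** A default of treatment-emergent is sensible when onset relative to dosing is unknown. Here the protocol has the site answer that question on the AE form, and the SAP applies the default whatever the answer. The item is most useful when the date is partial, and those are the cases in which the rules leave it out.

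The number of AEs is an additional secondary endpoint, and the AE tabulations in protocol 14.3.8.1 are restricted to treatment-emergent events. A screening or wash-out event that the site knew to be pre-dose would be reported as on-treatment. This could include an AE of special interest or a serious AE.

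**Working it through.** The plan gives no figure to reproduce, so the check applies the SAP 6.9.3 rules literally and compares the result with protocol 14.3.8.1.

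**Test records.** First dose is on 20 March, true onset is before dosing, and the site has marked the AE as pre-dose.

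| Recorded start | Recorded end | SAP 6.9.3 | Protocol 14.3.8.1 |
|---|---|---|---|
| March, day missing | 15 March | not treatment-emergent | not treatment-emergent |
| March, day missing | 25 March | treatment-emergent | not treatment-emergent |
| March, day missing | ongoing | treatment-emergent | not treatment-emergent |
| March, day missing | March, day missing | treatment-emergent | not treatment-emergent |
| Same year, month missing | ongoing | treatment-emergent | not treatment-emergent |

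The two documents disagree in four of the five records. The worsening clause does not reconcile them, because a worsening has its own AE record and the pre-dose record is not that event.

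**Was the definition changed on purpose?** The SAP Introduction lists what was introduced after the protocol: the meningococcal response definition, two analyses of the EASI score and the per protocol set. The treatment-emergent definition is not listed.

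**How often could the rules be reached?** Assume first-dose dates spread evenly over a year and onsets spread evenly over screening. The share of pre-dose days in the same calendar month as first dose is about 75% for a 14-day screening period and 35% for 42 days. In the same calendar year it is about 98% and 94%. So a pre-dose AE with a partial start date will often meet one of the two rules.

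**What share of year-only AEs is truly pre-dose?** Take first dose on 1 July and onset uniform over the days on which AEs are collected in that year. Pre-dose days are 14 to 42 (screening only). Post-dose days to 31 December are 184, which lies within the 30 weeks (210 days) to the end of follow-up.

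- Share = pre / (pre + post): 14/(14 + 184) = 14/198 = 7%, up to 42/(42 + 184) = 42/226 = 19%.
- If the subject leaves at Week 16 (16 × 7 = 112 days): 14/126 = 11%, up to 42/154 = 27%.

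**Effect on comparisons.** Let a and b be the expected treatment-emergent counts in the two arms, and let m be the expected number of misclassified pre-dose events per arm, equal under 1:1 randomisation.

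- Difference: (a + m) − (b + m) = a − b, unchanged.
- Ratio: (a + m)/(b + m) moves towards 1.
- Subject percentages: suppose a fraction q of subjects in each arm has such an event, independently of their other AEs. A percentage p becomes p + (1 − p)q, and the difference becomes (p₁ − p₂)(1 − q), a small shrinkage when q is small.

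**The case against.** The strongest reply is that counting uncertain onset as treatment-emergent is a usual conservative convention, and that very few records can be affected. A record must have a partial start date, match the month or year of first dose, be marked pre-dose and not be shown to have ended before dosing. Sites must report a start date, subjects are asked about AEs at screening and on Day 0, and discrepant data are queried. All AEs are listed, and each serious AE or AE of special interest has a narrative. The SAP also says that it supplements the protocol, so the protocol definition could be said to govern.

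The point about size stands. The point about convention stands only where onset is truly unknown; it does not justify setting aside a recorded answer. Programmers may use the item in practice, but the SAP does not say so, and its rules as written give the opposite result.

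Three stronger readings are tempting and not supported:

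- A reader might infer that, with first dose on 1 July, about half of year-only AEs began before dosing. That would need collection from 1 January. Collection starts at consent, which gives the 7–19% (or 11–27%) shown above.
- A reader might infer that the rule pulls every between-arm difference towards zero. It does not change the expected difference in AE counts.
- A reader might infer that the SAP uses the item for AEs on the day of first dose and ignores it elsewhere. SAP 6.8.1 names no variable. With no start time listed in protocol 13.3, the item is probably needed there, but that is inference.

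**Conclusion.** The point holds as a narrow conflict between the SAP and the protocol. In the same-month and same-year rules of SAP 6.9.3, an AE recorded as pre-dose is treatment-emergent unless its end information precedes exposure start. Protocol 14.3.8.1 would not count it.

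AEs with complete dates are outside these two rules, as are AEs with a missing day in an earlier month or a missing month in an earlier year. The documents do not say how many AEs will have partial dates, so the absolute size is unknown and probably small. Where it occurs, it adds known pre-dose events to the tables of both arms, inflates counts and slightly dilutes ratios and subject percentages. The expected difference in counts stays the same, given randomisation and equal completeness of AE dating in the two arms. The primary and efficacy endpoints are unaffected.

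**What to change.** In SAP 6.9.3, change only two AE bullets: same month with the day missing, and same year with the month missing. Add to each: *or unless the AE form records onset before the first tralokinumab/placebo dose, in which case the AE is not treatment-emergent; a later worsening counts through its own AE record*.

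- Keep the treatment-emergent default when the item is blank or says not prior.
- Leave all other month, year and period-assignment rules as they are. It would be a mistake to apply them only when the item is blank: they also place post-dose AEs in the treatment or follow-up period, and a mistaken tick could then override a known later month or year.
- Query any record in which the item contradicts the known part of the date.
- State in SAP 6.8.1 that the same item decides AEs starting on the day of first dose when no start time is available.

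The cost is one clause in each of the two bullets, one sentence in 6.8.1 and one programming condition. No new data are needed.
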